## **I. Abbreviations**

AFNI	Analysis of Functional Images
BIRC	Brain Imaging Research Center
fMRI	Functional Magnetic Resonance Imaging
PFC	Prefrontal Cortex
PTSD	Posttraumatic Stress Disorder
SCR	Skin Conductance Response

## **II. Protocol Summary**

State of the art treatments for posttraumatic stress disorder (PTSD) are only associated with success rates of ~60% (Foa, et al., 1999; Foa, Rothbaum, Riggs, & Murdock, 1991; Schnurr, et al., 2007). The goal of this project is to test a novel means of boosting efficacy of exposure-based therapy for PTSD.

## **III. Background and Rationale**

PTSD is characterized by intense emotional distress upon exposure to trauma reminders and avoidance of people and places that can trigger the trauma memory. Neurocircuitry models of PTSD that seek to explain symptoms of heightened emotional reactivity, hypervigilance for threat, and avoidance (Patel, Spreng, Shin, & Girard, 2012; Rauch, Shin, & Phelps, 2006) suggest abnormal activity of neural regions involved in emotional reactivity (e.g., amygdala) and cognitive control of emotional responding (e.g., ventral medial prefrontal cortex, anterior cingulate cortex). While knowledge exists about neurobiological abnormalities associated with PTSD, these data are cross-sectional in nature and ignore individual differences in both neural encoding and subjective aspects of the trauma itself (e.g., whether it elicits fear vs guilt vs disgust). Additionally, the manner by which existing psychological treatments alter these neural mechanisms mediating core PTSD symptoms is unknown. This is problematic, given that state-of-the-art treatment for PTSD is only effective ~60% of the time (Foa et al., 1991; Schnurr et al., 2007).

Here, we propose to utilize a novel computational modeling approach combined with state-of-the-art fMRI-based neurofeedback (S. LaConte, Strother, Cherkassky, Anderson, & Hu, 2005; S. M. LaConte, 2011; S. M. LaConte, Peltier, & Hu, 2007) to directly identify and modulate the idiosyncratic neural network encoding the trauma memory. Successful pursuit of these aims would 1) provide scientific support for the hypothesis that a distributed network including the amygdala, hippocampus, medial PFC, lateral PFC, and anterior insula mediates emotional responding upon trauma memory recall, and 2) provide proof-of-concept evidence that neurofeedback modulation of this network can boost existing therapy efficacy.

## **IV. Hypothesis or Research Question /Specific Aims**

**Overall research goals:** The overall goals of this research plan are to:

- 1) Develop a computational model that identifies idiosyncratic neural networks mediating emotional responding upon trauma memory recall. *Hypothesis:* Co-activation between amygdala, hippocampus, medial PFC, lateral PFC, and anterior insula mediates emotional responding upon trauma memory recall.
- 2) Demonstrate that real-time fMRI neurofeedback of the identified idiosyncratic brain network modulates the activity of the brain network, which in turn corresponds with expected changes in objective measures of emotional arousal. *Hypothesis:* Neurofeedback increases or decreases activity of the identified neural network, resulting in increases or decreases in emotional arousal, respectively.

## V. Trial Design

### Overview

There are two stages to this experimental protocol: Pilot Stage and Implementation Stage. In the pilot stage, we would recruit healthy adult women (n=10). In the implementation stage, we would recruit adult women with a history of physical or sexual assault or trauma (n=17). The pilot stage will be used to refine the methodology prior to enrolling the more vulnerable assault sample in the implementation stage. All procedures between the different stages would be conceptually identical.

Participants would have two visits to the BIRC. On day 1, participants would undergo a structured clinical interview to assess trauma history and mental health diagnoses. Participants would also complete assessments and a standardized form for generating idiosyncratic trauma/stress scripts. Participants would return on Day 2 in order to complete the MRI scan. The MRI scan will consist of a resting state scan and neurofeedback scans. The neurofeedback scans will consist of two phases: model building and neurofeedback phases. During the model building phase, participants would be presented their stress/trauma scripts in concurrent visual and oral formats during fMRI while undergoing simultaneous measurement of physiological arousal (SCR). A computational model would be fit to this initial data to identify the brain regions that correspond with heightened emotional arousal during the stress/trauma script. Participants would then be given three neurofeedback phases (3 minutes each), during which they are given feedback to decrease, increase, and decrease activity in this network. A more detailed description is included in the following section.

### fMRI Procedures

Prior to the MRI scan, subjects may have a training session in the MRI simulator to help habituate and train them to the MRI environment and MRI tasks. During this training session, subjects will also be allowed to practice some of the computer tasks. Per the MRI Policies and Procedures, the decision of who will be acclimated in the MRI Simulator will be made by the Research Coordinators and PI on a case-by-case basis. The PI for the study will have final say in this decision.

Before the MRI scan, participants will be given an explanation of the study's procedures and screened with the MRI Safety Form for metal objects and claustrophobia. Participants will also be screened with the SAFESCAN® ferromagnetic detector according to MRI Policy and Procedures. The participant will then lie supine in the scanner. Participants will wear noise-cancelling headphones for communication and view visual stimuli through a mirror attached to the imaging head coil. Participants will undergo an anatomic scan in addition to functional scans to facilitate alignment of images.

*Script generation.* Numerous studies have used script-guided imagery to induce emotional states, including creation of stress scripts, neutral scripts, and trauma scripts to induce generic emotional distress or emotional distress specific to trauma memory recall vs neutral scripts (Cisler, et al., 2014; Orr, et al., 1998; Orr, Pitman, Lasko, & Herz, 1993; Pitman, Orr, Forgue, de Jong, & Claiborn, 1987; Rauch, et al., 1996; Shalev, Orr, & Pitman, 1992, 1993; Sinha, Garcia, Paliwal, Kreek, & Rounsaville, 2006; Sinha, Lacadie, Skudlarski, & Wexler, 2004). Here, we would use this standardized methodology to activate a stress memory (pilot stage participants only) or a trauma memory (implementation stage participants only) during fMRI. During the Day 1 assessments, participants will be asked to write a short narrative (including about 500 words) describing a stressful/traumatic event using standardized methodology. This narrative will be displayed both on screen and via audio recording through headphones during the MRI scan. The pilot stage participants would create a non-traumatic stress script based on selecting a recent real-life stressful experience, while the implementation stage participants would create a trauma script describing their primary traumatic event. These procedures are consistent with our previous IRB approved protocols (133973 and 202715).

*Real-time fMRI and neurofeedback.*

*Modeling building phase.* The first phase of the MRI acquisition would consist of a single 3 min presentation of the stress/trauma script followed by a 3 min presentation of the neutral script (with the order counterbalanced across participants). In between the stress/trauma script and neutral script, there would be an emotion rating period, during which the participants indicate on a 9 pt Likert scale their anxiety and vividness of the imagery. Skin conductance response (SCR) will be recorded using BIOPAC's psychophysiological monitoring equipment. A series of electrodes placed on the participant's skin will measure SCR and provide an objective measure of physiological arousal. A subsequent reinforcement learning algorithm, fitted Q learning, would be applied to these joint fMRI and SCR data to identify distributed patterns of co-activated brain regions that specifically encode high emotional arousal (i.e., high SCR) to the stress/trauma memory. The resulting idiosyncratic brain map would inform the neurofeedback phase in the next three runs. This phase will take approximately 6 minutes.

*Neurofeedback phase.* In this phase, participants would undergo three additional 3 min presentations of the stressful/traumatic script; however, they would also concurrently be given neurofeedback to up- or down-modulate the identified brain network. In this neurofeedback phase, participants would be given visual feedback of the current state of their brain with

respect to the desired brain state (based on the computational model). In order to demonstrate a causal relationship between the brain state and emotional arousal, we would alternate between instructions to decrease the brain state (during which we expect to see decreased SCR), increase the brain state (during which we expect to see heightened SCR), and then decrease the brain state again. The sequence of manipulations would always be decrease – increase – decrease so that participants always end during a phase attempting to decrease emotional arousal. Also note that other experiments have used neurofeedback to modulate pain and both increase and decrease pain in order to demonstrate experimental control of pain through manipulation of the identified brain regions (deCharms, et al., 2005). This phase will take approximately 18 minutes.

The visual representation of the brain network will be presented using each participant's stress/trauma stress. The script will be typed and presented to the participant while laying in the scanner. During Run 1 (initial acquisition), participants will be instructed to focus on the memory and any thoughts or feelings associated with it. During Runs 2, 3, and 4, participants will be instructed to either increase or decrease emotional arousal, based on instructions given to them. The script will increase or decrease in brightness as activation of the brain state increases or decreases. Participants learn to control activation of their brain state, and thus the brightness of the script, through trial and error on their own. Figure 2 provides an overview of the experimental design while participants undergo fMRI.

[figure not shown]

Figure 2. Diagram depicting Model-building and Neurofeedback Phases

Image acquisition is performed by a Philips Achieva 3T X-series MRI.

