### **MRI**

Upon arrival to the BIRC for the fMRI scanning session, the participant will be given instructions for what they will be asked to do in the scanner. Prior to the scan, participants will complete the Strategies to Increase and Decrease Emotions form. Following the training, the participant will be screened for internal metal and claustrophobia. The participant will also be screened using the SAFESCAN® ferromagnetic detector per MRI Protocol and Procedures. The fMRI data will be acquired on a 3T Achieva X-series head-dedicated MRI scanner (Philips Healthcare, USA). The lead MRI coordinator has had extensive experience with high field imaging systems. Training on the current system was given to the coordinator by a Philips education specialist. A similar training was given to the back-up coordinator as well. Each MRI session will start with a localizer and reference scan to optimize head placement. Experimental tasks will be programmed with commonly used software (Presentation), and the images will be projected onto a translucent screen via a projector situated in an adjacent room. Anatomic fMRI scans will be acquired on all subjects for image alignment purposes.

**Assessing participant well-being:** The PI will be present at each scan. A clinical psychologist with significant PTSD experience will assess the participant's emotional well-being in person immediately following the scan with a private and informal clinical interview. Referral information about treatment options and contact information will be provided to participants who need it. Additionally, a trained research coordinator will contact the participants approximately one week later by phone to assess well-being. Referral information about treatment options and contact will be given to participants who need it. This research coordinator will have access to the clinical psychologist for questions regarding participants' clinical status.

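### Instruction and feedback always change together in Runs 2-4, so the planned comparisons cannot show that feedback of the network, or the network itself, causes the change in arousal

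*Combined protocol and SAP*

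**What the plan says.** All references are to the combined protocol and SAP.

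- **Purpose of the runs.** Section V, fMRI Procedures (Neurofeedback phase), gives the reason for alternating the direction: "In order to demonstrate a causal relationship between the brain state and emotional arousal". The hypothesis under goal 2 in Section IV is also causal: "Neurofeedback increases or decreases activity of the identified neural network, resulting in increases or decreases in emotional arousal, respectively". The goal itself is worded more softly, as a network change "which in turn corresponds with expected changes in objective measures of emotional arousal".
- **Instruction.** The Neurofeedback phase paragraph says "we would alternate between instructions to decrease the brain state (during which we expect to see decreased SCR), increase the brain state". The text that follows on Runs 2, 3 and 4 says "participants will be instructed to either increase or decrease emotional arousal, based on instructions given to them".
- **Feedback.** In all three runs the brightness of the script follows the decoded brain state. The order is always decrease, increase, decrease. No run with sham feedback, or with the instruction but no feedback, is described.
- **Decoder.** It is fitted to the model-building data so that voxel activity predicts SCR (Sections V and XII).
- **Analysis.** Section XII compares mean brain state and SCR across the instruction conditions by repeated measures GLMs. The power statement covers only changes between the phases.
- **Strategies form.** Section VII, MRI: "Prior to the scan, participants will complete the Strategies to Increase and Decrease Emotions form".
- **Wider claim.** Section III expects proof of concept that "neurofeedback modulation of this network can boost existing therapy efficacy".

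**The concern.** A causal reading of Runs 2-4 needs something that separates the feedback from the instruction that comes with it. Here the two change direction together in every run. If participants are told to raise or lower arousal, they are told to produce the outcome. Someone who can do this unaided would shift SCR. Because the decoder was built to predict SCR, the decoded brain state would be expected to shift with it. The study would then show exactly the pattern it predicts, whatever the feedback contributed.

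There is a second gap. Two mean comparisons by instruction can both be positive without showing that the two measures move together within participants. Aim 2 speaks of correspondence, and nothing planned for Runs 2-4 tests it.

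At stake is what a positive result may be said to mean. The instruction wording also has to be settled before scanning, because data collected under the arousal instruction cannot be repaired afterwards.

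**Working it through.** **1. The plan's own power figure.** Section XII gives n = 17, large effects and power above .8. It states no effect size or alpha. Assume a paired comparison with dz = 0.8 and two-sided alpha 0.05:

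- noncentrality = dz × √n = 0.8 × √17 = 3.30; df = 16; critical t = 2.12
- power = P(|t| > 2.12) under the noncentral t = 0.872

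The three-level repeated measures F-test with f = 0.40 and sphericity gives 0.68, 0.84, 0.94 and 0.996 at within-subject correlations of 0, 0.3, 0.5 and 0.7. The stated figure is therefore reproduced under usual readings of a large effect. It is power for a difference between instruction conditions, from whatever source.

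**2. The same test if feedback adds nothing.** Suppose the instruction alone shifts SCR by dz. The documents give no value for this, so a range is shown (n = 17, two-sided 0.05):

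| Assumed instruction-only dz | dz × √17 | P(increase-versus-decrease SCR comparison significant) |
|---|---|---|
| 0.2 | 0.82 | 0.12 |
| 0.3 | 1.24 | 0.21 |
| 0.5 | 2.06 | 0.49 |
| 0.8 | 3.30 | 0.87 |

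**3. Both planned outcomes together.** In a simulation of 20,000 trials of 17 participants, the instruction moves arousal, and arousal moves both brain state and SCR. Neither the network nor the feedback affects SCR. The instruction shift is 0.7, and the run-level noise SD is 0.5 for arousal and 0.5 for each measure. The increase-minus-mean-decrease contrast has variance (0.25 + 0.25) × (1 + ½) = 0.75, so dz = 0.7/√0.75 = 0.81. The brain-state contrast was significant in 88% of trials, the SCR contrast in 88%, and both in 80%.

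**4. Which instruction applies.** One paragraph names the brain state as the target and the next names emotional arousal. Under the second, the instruction is to change the outcome. Under the first, the outcome is not named, but instruction and feedback target still change together. The inference is limited on either reading, and more so on the second.

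**5. Could an added link test rescue the causal claim?** No. In the simulation of step 3, where the network has no causal role, the change scores in brain state and SCR still correlated at about 0.49 on average and were significant in 56% of trials. A within-run version fares no better. With a shared, autocorrelated arousal signal (AR(1) 0.7, 90 samples per run, three runs, 17 participants, unit noise SD) and weak loadings of 0.2 on brain state and 0.4 on SCR, the run-centred slope was significant in about 99% of trials with no brain-to-SCR effect. With loadings of 0.3 and 0.5 it was significant in essentially all of them. Such a test can show correspondence, not cause.

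**The case against.** The strongest case on the other side is that this is a proof-of-concept study of 10 plus 17 women, in which a missing feedback control limits inference without invalidating the study. The Neurofeedback phase paragraph itself describes the last run as an attempt to lower emotional arousal, so the arousal instruction may be loose shorthand. Aim 2's goal claims only correspondence. These points lower the weight of the concern. They do not remove the causal purpose stated in Section V or the causal hypothesis in Section IV.

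A reader might also infer more than the documents support:

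- *That a positive result would be fully explained by the instruction.* The design does not separate instruction from feedback. It does not show that feedback contributes nothing. Could be explained is as far as one can go.
- *That the link between brain state and SCR is never tested.* Section XII fits and cross-validates it in model building. It is untested only in the neurofeedback runs.
- *That a false attribution is as likely as a true one.* The 0.87 is ordinary power at an assumed dz of 0.8. It falls to 0.21 at 0.3, and comparing true with false attributions would need prior probabilities that nobody has.
- *That the strategies form contradicts learning by trial and error.* Section V, Assessments, describes the form as covering strategies for changing brain states. Listing candidate strategies and then finding out which ones work is compatible with that.
- *That therapy benefit is a tested claim.* Section III says proof of concept, Section IX says potentially and disclaims direct benefit to participants, and no aim tests therapy. It is background framing, although no therapy is given and no symptom outcome is specified after the scan.

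Figure 2 is not available, so a control run shown only there cannot be excluded. The text describes none.

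**Conclusion.** The concern holds in this form. Runs 2-4 are meant to show that brain state causes arousal, but instruction and real feedback always change together, with no sham or instruction-only run described and a decoder trained on SCR. Voluntary regulation alone could give the predicted result. How often depends on an unknown instruction-only effect: 0.21, 0.49 or 0.87 for the SCR comparison at dz 0.3, 0.5 or 0.8, assuming n = 17, a paired contrast and two-sided 5%. The stated power is not wrong. It answers a different question from the causal one. Separately, the two descriptions of the instruction conflict, and the correspondence in Aim 2 has no test in Runs 2-4.

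The planned comparisons remain valid for the joint effect of instruction plus feedback, subject to the fixed run order. The increase-minus-mean-decrease contrast cancels a linear time trend but not a curved one.

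**What to change.** 1. **One instruction.** Reconcile the two descriptions in Section V so that a single instruction applies, preferably to change the feedback signal (script brightness) rather than arousal. Cost: script wording. Self-regulation may be somewhat harder to learn. This removes the direct instruction to produce the outcome, but does not by itself separate instruction from feedback.
2. **Narrower conclusion.** Replace the causal purpose in Section V and the causal hypothesis in Section IV with the joint effect of instruction plus feedback on network activity and SCR in assault-exposed women. Do not present a boost to therapy as something this study will show. Cost: wording only. If the causal claim is to stay, a control condition, such as the same instruction without feedback or with sham feedback, would be needed.
3. **Test of correspondence.** Add a mixed model of SCR on run-mean-centred decoded brain state within Runs 2-4, with run/instruction as fixed effects and participant as a random effect. State in advance that it tests Aim 2's correspondence and is not evidence of causation, because spontaneous arousal can drive both signals. Cost: one model on data already collected.

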### **Assessments**

Participants will complete several interviews and questionnaires to determine psychological and medical history, current life functioning, history of drug use, stress experiences, individual traits, family functioning, and demographic variables.

*Structured Clinical Interview for DSM-IV:* measures current psychological functioning and drug use history (First et al., 2002).

*Data Collection Form:* internal form used to collect study specific information such as handedness, age, race/ethnicity, medications, etc.

*National Survey of Adolescent Trauma Assessment:* assesses assaultive event exposure and other types of childhood adversity history and chronology (Kilpatrick, et al. 2000, Kilpatrick, et al. 2003).

*Beck's Depression Inventory:* measures the severity of current depression (Beck et al., 1961).

*Childhood Trauma Questionnaire:* measures histories of abuse and neglect during childhood (Bernstein, et al. 2003).

*Difficulty in Emotion Regulation Scale:* assesses multiple aspects of emotion dysregulation (Gratz & Roemer, 2004).

*NEO Five-factor Inventory:* measure of the Big Five personality traits (Goodwin and Friedman 2006).

*Positive and Negative Affect Scale:* measure of current (at this moment) affect (Watson et al., 1988).

*Posttraumatic Stress Disorder Checklist- 5:* assesses the 20 DSM-5 symptoms of PTSD (Weather et al., 2013).

*Strategies to Increase and Decrease Emotions:* provides information about various strategies participants may use to increase or decrease activation of brain states.

*Stress Script Generating Forms:* create narrative description of stressful/traumatic events (Pitman et al., 1987). This form is identical to forms used in previously approved projects (IRB#: 113160, 133973, and 202715).

